8.7.2 Analysis of the secondary variable(s)

Duration of response

Duration of response in responding patients will be summarised and the number (%) of responding patients with a duration of response >3; >6; >9; >12; >18 and >24 months will be presented. A Kaplan Meier plot and median duration of response with 95% CI (calculated from the Kaplan Meier plot) will be presented. DCR will be summarised. DoR and DCR will be presented based on the ICR, and as a sensitivity analysis they will be present based on the investigator assessment.

Tumour shrinkage

The best absolute change in target lesion tumour size from baseline and percentage change in target lesion tumour size from baseline will be summarized using descriptive statistics and presented at each timepoint.

Tumour size will also be presented graphically using waterfall plots, to present each patient's best percentage change in tumour size as a separate bar, with the bars ordered from the largest increase to the largest decrease. Reference lines at the +20% and -30% change in tumour size levels will be added to the plots, which correspond with the definitions of progression and 'complete or partial' response respectively.

The mean and median best change from baseline in tumour size will be summarized. This will also be summarised for week 6 and week 12 data.

To assess the depth of tumour shrinkage, the proportion of patients who achieve >30%, >50% and >75% reduction in target lesions will be summarised descriptively.

Tumour shrinkage will be presented based on the primary reader ICR data, and as a sensitivity analysis they will be present based on the investigator assessment.

Disease control rate (DCR)

BoR of disease control rate (DCR) by ICR in the evaluable for response analysis set will be presented together with 95% exact (Clopper Pearson) confidence intervals.

Additional summaries of DCR will be performed

- DCR by investigator assessment
- DCR by EGFR mutation subtype: Exon 19 deletion/L858R/Other.
- DCR in the subgroup of patients who received TKI as last treatment prior to study start and those whose treatment prior to study start was not a TKI

The concordance between DCR as assessed by ICR and by investigator will be presented.

Progression Free Survival (PFS)

PFS will be displayed using a Kaplan-Meier plot. The number events, median (calculated from the Kaplan Meier plot), and the proportion of patients without an event at 6, 12, 18 and 24 months summarised. PFS will be presented based on the ICR assessments, and as a sensitivity analysis PFS will be presented based on the investigator assessment.

Overall Survival (OS)

When there is sufficient data (>20 events), OS will be displayed using a Kaplan-Meier plot. The number events, median (calculated from the Kaplan Meier plot), and the proportion of patients without an event at 6, 12 and 18 months will be summarised.

As appropriate, summaries of the number and percentage of patients who have died, are still in survival follow-up, are lost to follow-up and have withdrawn consent will be presented.

HRQoL and symptoms

Time to symptom deterioration

For each of the 6 symptoms scales/items in QLQ LC13 (dyspnoea, cough, haemoptysis, chest pain, arm/shoulder pain, other pain) time to deterioration in symptoms will be presented using a Kaplan-Meier plot. Summaries of the number and percentage of subjects experiencing a clinically meaningful deterioration or death, and the median time to deterioration will be also be provided. The proportion of patients alive and free from symptom deterioration at 3, 6, 12 and 24 months will be summarized using the Kaplan-Meier estimates.

Symptom Improvement Rate

For each of the symptom scales/items in QLQ LC13, a 95% confidence interval for symptom improvement rate will be constructed using the Newcombe-Wilson method. In addition, the change from baseline at each assessment time point (in terms of proportion of patients improved, stable, and worsened as defined in Section 8.4) and the mean change from baseline scores at each time point will be summarised for all symptom scales/items from the QLQ LC13 and QLQ-C30.

Definition of clinically meaningful changes

For each functional scale in the QLQ-C30 (physical, role, emotional, cognitive, social) and for Global Health status, the change from baseline at each assessment time point (in terms of proportion of patients improved, stable, and worsened as defined in Section 8.4) and the mean change from baseline scores at each time point will be summarised.

Safety Assessments

Safety and tolerability data will be presented using summaries and descriptive statistics, as detailed in the SAP.

AEs (both in terms of MedDRA preferred terms and CTCAE grade) will be listed individually by patient. The number of patients experiencing each AE will be summarised by CTCAE grade.

Other safety data will be assessed in terms of physical examination, clinical chemistry, haematology, vital signs and LVEFs.

Exposure to AZD9291 will be summarised. Time on study and AZD9291 dose reductions and dose delays will also be summarised.

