8. STATISTICAL ANALYSES BY ASTRAZENECA

8.1 Statistical considerations

A comprehensive Statistical Analysis Plan (SAP) will be prepared prior to first subject enrolled. All Analyses will be performed by AstraZeneca or its representatives. Additional details relating to the Independent Central Review will be detailed in the Independent Central Review Charter.

The data cut-off for the primary analysis of ORR will take place 18 weeks after the last subject enrolled, to allow opportunity for all patients to complete two RECIST follow-up assessments. At this time, DoR and safety/tolerability will also be summarised. The primary analysis CSR will report the analysis of ORR supported by duration of response, and safety and tolerability data.

The full CSR will report the analysis of all primary and secondary endpoints (including updated ORR and DoR, DCR, tumour shrinkage, PFS, OS, Safety and HRQoL) and summarise the exploratory endpoint of patient reported adverse events (PRO-CTCAE). The data cut-off for this analysis will take place approximately 12 months after the last subject has been enrolled, to allow responding patients to have a DoR greater than 6 months.

All patients will continue to be followed up in order to capture the reliable overall survival data based on a final data cut-off when approximately 95 OS events (about 55% maturity) have been observed out of all enrolled. The final analyses will include the analysis for OS PRO and Safety data at this DCO. Analysis for RECIST related endpoints (ORR, DoR, tumor shrinkage, DCR and PFS) cut-off at RECIST modules freeze time will be also performed at final analysis.

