ORR rate is defined as the number (%) of subjects with measurable disease with at least one visit response of CR or PR that is confirmed at least 4 weeks later (according to ICR for the primary analysis). Data obtained up until progression, or last evaluable assessment in the absence of progression, will be included in the assessment of RR. However, any complete response or partial response which occurred after a further anticancer therapy was received will not be included in numerator of the ORR calculation.

In the case where a subject has two non-consecutive visit responses of PR, then, as long as the time between the 2 visits of PR is greater than 4 weeks and there is no PD between the PR visits, the subject will be defined as a responder. Similarly, if a subject has visit responses of CR, NE, CR, then, as long as the time between the 2 visits of CR is greater than 4 weeks, then a best response of CR will be assigned.

Duration of Response (DoR)

Duration of response will be defined as the time from the date of first documented response, (that is subsequently confirmed) until date of documented progression or death in the absence of disease progression, the end of response should coincide with the date of progression or death from any cause used for the PFS endpoint. The time of the initial response will be defined as the latest of the dates contributing towards the first visit response of PR or CR. If the response is not confirmed, it will not be included.

If a subject does not progress following a response, then their duration of response will use the PFS censoring time.

Disease control rate (DCR)

Disease control rate is defined as the percentage of patients who have a BoR of CR or PR or SD.

Tumour Shrinkage

Tumour shrinkage will be assessed using RECIST tumour response. The absolute change and percentage change from baseline in sum of tumour size at each assessment will be calculated. The best change in tumour size will include all assessments prior to progression or start of subsequent anti-cancer therapy.

Progression Free Survival (PFS)

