8.7 Methods for statistical analyses

All data will be presented for the overall full analysis set/evaluable for response set (as appropriate), and also by two cohorts defined by line of treatment; TKI treatment only / previous TKI and a platinum-based doublet chemotherapy (patients may have also received additional lines of treatment).

Descriptive statistics will be used for all variables, as appropriate. Continuous variables will be summarised by the number of observations, mean, standard deviation, median, minimum, and maximum. Categorical variables will be summarised by frequency counts and percentages for each category. Unless otherwise stated, percentages will be calculated out of the full analysis set.

Baseline will be the last assessment of the variable under consideration prior to the intake of the first dose of investigational product, except for efficacy variables. For efficacy variables, baseline is defined as the last visit prior to enrolment.

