8.7.4 Planned Analyses

No interim analyses are planned for this study.

The primary analysis of ORR will take place after all patients have completed at 18 weeks after the last subject enrolled, to allow opportunity for all patients to completed two RECIST follow-up assessments. At this time, DoR and safety/tolerability will also be summarised. The primary analysis will report the analysis of ORR supported by duration of response, and safety and tolerability data.

The full analysis will report the analysis of all primary and secondary endpoints (including updated ORR and DoR, DCR, tumour shrinkage, PFS, OS, Safety HRQoL) and summarise the exploratory endpoint of patient reported adverse events (PRO-CTCAE). This analysis will take place approximately 12 months after the last subject has been enrolled, to allow responding patients to have a DoR greater than 6 months.

All patients will continue to be followed up in order to capture the reliable overall survival data based on a final data cut-off when approximately 95 OS events (about 55% maturity) have been observed out of all enrolled patients. The final analyses will include the analysis for OS and Safety data at this DCO. Analysis for RECIST related endpoints (ORR, DoR, tumor shrinkage, DCR and PFS) cut-off at RECIST modules freeze time will be also performed at final analysis as presented in the table below.

Table 9 Endpoint for final analysis and related data extraction time

Data extraction time	Endpoints
RECIST modules freeze time (24 months post LSFD)	ORR DoR Tumor shrinkage DCR PFS PFS2* time to subsequent treatment*
Final DCO (when reach approximately 95 OS events)	OS, PRO and safety

*Exploratory analysis

An earlier summary of ORR (before all patients have completed two RECIST follow-up assessments) could be performed at the request of regulatory authorities or AZD9291 Steering Committee.

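### Duration-of-response landmarks are planned as crude percentages of responders, so they run low wherever follow-up is shorter than the landmark: mainly at the 18-week cut-off and for late landmarks afterwards

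*Protocol*

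**What the plan says.** For DoR, section 8.7.2 of the protocol says that "the number (%) of responding patients with a duration of response >3; >6; >9; >12; >18 and >24 months will be presented". The following sentence reads: "A Kaplan Meier plot and median duration of response with 95% CI (calculated from the Kaplan Meier plot) will be presented". Kaplan-Meier is thus named for the plot and the median, but not for the landmarks.

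Section 8.4 fixes the value for a responder with no event: "If a subject does not progress following a response, then their duration of response will use the PFS censoring time". Section 8.7 sets the general rule for categories: "Categorical variables will be summarised by frequency counts and percentages for each category". For time to symptom deterioration, section 8.7.2 does name the method: "The proportion of patients alive and free from symptom deterioration at 3, 6, 12 and 24 months will be summarized using the Kaplan-Meier estimates".

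DoR is reported at three cut-offs. Section 8.1 says "The data cut-off for the primary analysis of ORR will take place 18 weeks after the last subject enrolled", with DoR summarised then in support of ORR. The full analysis follows about 12 months after last enrolment. The last RECIST cut-off is 24 months after the last subject's first dose (section 8.7.4, Table 9). Under sections 5.1.1 and 5.1.2, scans and tumour data are no longer collected after that.

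**The concern.** DoR is right-censored. Under the definitions above, a responder censored at 10 months while still in response has a recorded DoR of 10 months. That patient is a responding patient, so belongs to the denominator, but cannot count towards >12, >18 or >24 months. The table would treat the patient like one who progressed at 10 months.

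Such a percentage mixes durability with time on study. The same landmark can rise from one cut-off to the next only because follow-up has lengthened. Durability carries much of the interpretation of a single-arm response-rate trial, and DoR is the efficacy measure reported beside ORR at the primary analysis. A low figure at a late landmark could be read as early loss of response when it mostly reflects recent enrolment.

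**Working it through.** **Inputs from the protocol.** Cut-offs at 18 weeks, about 12 months and 24 months after the last patient starts (sections 8.1 and 8.7.4; section 4.1 counts a patient as enrolled once treatment begins, so the origins coincide). Scans every 6 weeks from first dose (section 5.1.1), so the first response is seen nominally at week 6, which is 42/30.44 = 1.38 months.

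**Step 1: longest observable DoR of the last-enrolled responder** = cut-off minus time to first response. Eighteen weeks is 126/30.44 = 4.14 months.

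| Cut-off | Response at week 6 | Response at week 12 | Landmarks out of reach for this patient |
|---|---|---|---|
| 18 weeks | 4.14 − 1.38 = 2.8 months | 1.4 | all six |
| 12 months | 12 − 1.38 = 10.6 months | 9.2 | >12, >18, >24 |
| 24-month freeze | 24 − 1.38 = 22.6 months | 21.2 | >24 |

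This reproduces the plan's own figure: section 8.1 justifies the 12-month cut-off as letting responders reach a DoR above 6 months, and 10.6 and 9.2 both exceed 6. None of this step needs an assumption about accrual length or the DoR distribution.

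**Step 2: size.** Let F be potential follow-up from first response. If F is independent of DoR, the crude share beyond x is S(x) × P(F > x), whereas Kaplan-Meier targets S(x). The protocol gives neither accrual length nor a DoR distribution, so the following are assumptions: uniform accrual over 9 months, exponential DoR with median 9 months, response at week 6.

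| Cut-off and landmark | S(x) | P(F > x) | Crude |
|---|---|---|---|
| Primary, >3 | 0.794 | (2.76 + 9 − 3)/9 = 0.973 | 77% against 79% |
| Primary, >6 | 0.630 | (2.76 + 9 − 6)/9 = 0.640 | 40% against 63% |
| Primary, >9 | 0.500 | (2.76 + 9 − 9)/9 = 0.307 | 15% against 50% |
| Full, >9 | 0.500 | 1 | no difference |
| Full, >12 | 0.397 | (10.62 + 9 − 12)/9 = 0.847 | 34% against 40% |
| Full, >18 | 0.250 | (10.62 + 9 − 18)/9 = 0.180 | 4.5% against 25% |
| Freeze, >18 | 0.250 | 1 | no difference |
| Freeze, >24 | 0.157 | (22.62 + 9 − 24)/9 = 0.847 | 13% against 16% |

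**Step 3: range.** Over assumed medians of 6 to 18 months and accrual of 6 to 12 months, the crude figure is low by 3 to 14 points for >12 months at the full analysis, 8 to 50 points for >18 months at the full analysis, and about 1 to 9 points for >24 months at the freeze. The extremes for >18 months are: median 6, accrual 12, 0.125 × (10.62 + 12 − 18)/12 = 0.048 against 0.125; and median 18, accrual 6, where the longest follow-up is 10.62 + 6 = 16.62 months, so 0% against 50%.

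**Step 4: check with scan times.** A simulation with 100 responders, 6-weekly scans, median 12 months and accrual 9 months gave, Kaplan-Meier against crude: primary >6 months 73% and 39%; full >12 months 53% and 42%; full >18 months 36% and 1%; freeze >24 months 26% and 19%. It also shows the limit of Kaplan-Meier. At the primary cut-off nobody is followed to 18 months, and carrying the curve's last value forward gave 53% there, against 35% with complete follow-up.

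**The case against.** The strongest reply is that the crude row is only a supplement. The Kaplan-Meier plot and median handle censoring, and the probability of remaining in response can be read off the curve. No test or success rule uses a DoR landmark, and the study is sized on ORR precision. The error is conservative, because a count of responders seen beyond x months is a lower bound. Nor does the protocol say that all six landmarks appear at all three cut-offs; an SAP may choose rows or specify Kaplan-Meier estimates. All of this stands and limits the severity. It does not remove the fault, because the protocol wording fixes a count and percentage for these landmarks, and an SAP that followed it would produce the crude figures.

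Four stronger readings might be inferred and are not supported:

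- That durability as a whole is understated. Only the landmark percentages are; the median and curve are not.
- That every landmark is biased at every cut-off. For week-6 responders the cut-off costs nothing up to 9 months at the full analysis or up to 18 months at the freeze. A few later responders may fall short at >9 months in the full analysis: first response at week 12 and last scan at week 48 gives 36 weeks, about 8.3 months.
- That the PFS and OS landmarks share the error. Section 8.7.2 gives those as proportions without an event, in paragraphs built on Kaplan-Meier plots, and does not call them a number (%).
- That landmarks should be restricted to minimum follow-up. With at most 2.8 months for the last patient at the primary cut-off, this would suppress even >3 months, although Kaplan-Meier can validly use the patients followed longer.

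**Conclusion.** The point holds in limited form. As written, the DoR landmark percentages count responders censored before a landmark as not exceeding it, so they are too low wherever follow-up falls short. Which landmarks are affected follows from the protocol's own dates. The size does not: it depends on assumed accrual, DoR distribution and time to response, and ranges from a point or so for >24 months at the freeze to as much as 50 points for >18 months at the full analysis. The shortfall at >24 months will not mature, since tumour data collection ends at the freeze. This is a moderate reporting fault in a secondary endpoint that should be corrected; it does not affect ORR or the planned DoR median.

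**What to change.** In section 8.7.2, state that the probability of remaining in response at 3, 6, 9, 12, 18 and 24 months will be estimated by Kaplan-Meier, with a 95% CI and the number at risk at each landmark, as the same section already does by Kaplan-Meier for symptom deterioration. Show no estimate beyond the longest observed follow-up at that cut-off. If the crude counts are kept, label them as observed to date. The cost is a sentence in the protocol or SAP and a few table rows from a curve that is already planned; no extra data are needed.

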8.7.3 Subgroup analysis

All data summaries will be made by treatment cohort [previous TKI only/previous TKI and a platinum-based doublet chemotherapy (patients may have also received additional lines of

treatment)]. Summary of Chinese patients will be made combinedly and separately by treatment cohort.

8.7.4 Planned Analyses

No interim analyses are planned for this study.

The primary analysis of ORR will take place after all patients have completed at 18 weeks after the last subject enrolled, to allow opportunity for all patients to completed two RECIST follow-up assessments. At this time, DoR and safety/tolerability will also be summarised. The primary analysis will report the analysis of ORR supported by duration of response, and safety and tolerability data.

The full analysis will report the analysis of all primary and secondary endpoints (including updated ORR and DoR, DCR, tumour shrinkage, PFS, OS, Safety HRQoL) and summarise the exploratory endpoint of patient reported adverse events (PRO-CTCAE). This analysis will take place approximately 12 months after the last subject has been enrolled, to allow responding patients to have a DoR greater than 6 months.

All patients will continue to be followed up in order to capture the reliable overall survival data based on a final data cut-off when approximately 95 OS events (about 55% maturity) have been observed out of all enrolled patients. The final analyses will include the analysis for OS and Safety data at this DCO. Analysis for RECIST related endpoints (ORR, DoR, tumor shrinkage, DCR and PFS) cut-off at RECIST modules freeze time will be also performed at final analysis as presented in the table below.

Table 9 Endpoint for final analysis and related data extraction time

Data extraction time	Endpoints
RECIST modules freeze time (24 months post LSFD)	ORR DoR Tumor shrinkage DCR PFS PFS2* time to subsequent treatment*
Final DCO (when reach approximately 95 OS events)	OS, PRO and safety

*Exploratory analysis

An earlier summary of ORR (before all patients have completed two RECIST follow-up assessments) could be performed at the request of regulatory authorities or AZD9291 Steering Committee.

8.7.5 Sensitivity analysis

The same methods of analysis will be applied to analyse ORR, DoR, DCR and PFS based on the RECIST data assessed by the investigator.

8.7.6 Exploratory analysis

PRO-CTCAE

PRO-CTCAE data will be presented using summaries and descriptive statistics based on the Full Analysis Set and further details will be provided in the SAP.

Healthcare Resource Use

Healthcare Resource Use data will be presented using summaries and descriptive statistics, based on the Full Analysis Set and further details will be provided in the SAP.

Exploratory analysis of post progression endpoints

Up to RECIST modules freeze time (24 months post LSFD), PFS2 and time to subsequent treatment will be analysed using the same methods as the analysis of PFS and further details will be provided in the SAP.

Exploratory biomarker analysis

The comparison of each T790M status between results from the T790M screening test and the 3rd party kit (if data is available at time of analysis) will be performed and further details will be provided in SAP.

Summaries and analyses for other exploratory objectives will be documented in the study SAP and will be reported within the CSR.

9. STUDY AND DATA MANAGEMENT BY ASTRAZENECA

9.1 Training of study site personnel

Before the first subject is entered into the study, an AstraZeneca representative will review and discuss the requirements of the Clinical Study Protocol and related documents with the investigational staff and also train them in any study specific procedures and the WBDC and ePRO system(s) utilised.

The Principal Investigator will ensure that appropriate training relevant to the study is given to all of these staff, and that any new information relevant to the performance of this study is forwarded to the staff involved.

The Principal Investigator will maintain a record of all individuals involved in the study (medical, nursing and other staff).

